5.4.2 End of study

Subjects will follow study procedures until the end of the clinical study, death, withdrawal of consent from the study, and / or loss to follow-up. The study will end when the last subject has completed the long-term follow-up period or has died, whichever occurs first.

6. SUBJECT ELIGIBILITY

Subjects who meet all the inclusion criteria and none of the exclusion criteria will be included in this study:

6.1 Inclusion criteria

Male or female \geq 18 years old.

Able to understand, sign and date an informed consent form approved by the CEIC.

Advanced and / or metastatic colorectal cancer confirmed histologically or cytologically by the investigator.

KRAS non-mutated colorectal cancer.

At least 1 unidimensionally measurable lesion $>$ 10 mm with helical CT or $>$ 20 mm with conventional CT according to the revised RECIST 1.1 criteria. (All disease sites should be evaluated \leq 28 days before the start of treatment).

Patients with the following characteristics will be included:

1. Recurrence after adjuvant treatment +/- radiotherapy with a disease-free interval $>$ 6 months after completion.

2. De novo diagnosis of the disease.

ECOG (Eastern Cooperative Oncology Group) performance status of 0, 1 or 2. (recommended only 0-1)

Life expectancy \geq 3 months.

Adequate bone marrow function: neutrophils $\geq 1.5 \times 10^9 / L$; platelets $\geq 100 \times 10^9 / L$; hemoglobin $\geq 9 \text{ g / dL}$.

Liver, kidney and metabolic functions as follows:

Adequate liver function: ASAT (SGOT) and ALAT (SGPT) $2.5 \times \text{ULN}$ ($5 \times \text{ULN}$ if there are liver metastases). Total bilirubin $< 1.5 \times \text{ULN}$. Alkaline phosphatase $2.5 \times \text{ULN}$ ($5 \times \text{ULN}$ in case of liver metastases or $10 \times \text{ULN}$ in case of bone metastases).

Renal function, calculated as creatinine clearance or creatinine clearance for 24 hours $\geq 50 \text{ mL / min}$.

Magnesium $\geq \text{ULN}$, calcium $\geq \text{ULN}$.

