7.1.5. Warnings and precautions

Respiratory disorders

Individual cases of interstitial lung disease have been reported in which the causal relationship with cetuximab is unknown. If interstitial lung disease is diagnosed, cetuximab should be discontinued and the patient treated appropriately.

Skin reactions

If a patient develops a severe skin reaction (grade ≥ 3 ; US National Cancer Institute - Common Toxicity Criteria, NCI-CTC, v3.0), cetuximab treatment should be discontinued. Treatment can be resumed only if the reaction subsides to grade 2 (see section 4.8 of the product data sheet).

If the severe skin reaction has occurred for the first time, treatment can be resumed without change in dose.

If severe skin reactions occur for the second or third time, cetuximab should be stopped again. Treatment can be resumed at a lower dose (400 mg / m^2 after the second time, and 300 mg / m^2 after the third time) only if the reaction has subsided to grade 2.

If severe skin reactions appear for the fourth time, or they do not subside to grade 2 during treatment interruption, permanent discontinuation of cetuximab treatment is required.

Single-arm, multicenter, prospective phase II clinical trial for biomarker validation in patients with advanced and / or metastatic colorectal cancer with non-mutated KRAS gene treated with chemotherapy plus biweekly cetuximab as first-line therapy

Electrolyte disturbances

Progressive decreases in serum magnesium levels occur frequently, which can lead to severe hypomagnesemia. Hypomagnesemia is reversible after stopping cetuximab treatment. In addition, hypokalemia may occur as a result of diarrhea.

Hypocalcemia can also occur; in particular the frequency of severe hypocalcaemia may be increased when used in combination with platinum-based chemotherapy.

Serum electrolyte level determinations should be performed prior to treatment and periodically during treatment with cetuximab. Electrolyte replenishment is recommended as needed.

Neutropenia and related infectious complications

Patients receiving cetuximab in combination with platinum-based chemotherapy are at increased risk of severe neutropenia, which can lead to later infectious complications such as febrile neutropenia, pneumonia, or sepsis. Close monitoring is recommended in these patients, especially in those with skin lesions, mucositis or diarrhea, which may facilitate the development of infections (see section 4.8 of the product data sheet).

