Special populations

To date, only patients with adequate kidney and liver function (serum creatinine \leq 1.5 times, transaminases \leq 5 times and bilirubin \leq 1.5 times the upper limit of normal) have been studied.

Cetuximab has not been studied in patients with one or more of the following laboratory parameters:

- *hemoglobin <9 g / dl*
- *white blood cell count <3000 / mm³*
- *absolute neutrophil count <1500 / mm³*
- *platelet count <100,000 / mm³*

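### Protocol 6.1 sets the upper limit of normal as the minimum magnesium and calcium for entry, so patients with normal values are ineligible as written

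*Protocol*

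**What the plan says.** Protocol 6.1, in the list of liver, kidney and metabolic requirements, gives the limit as "Magnesium $\geq \text{ULN}$, calcium $\geq \text{ULN". The opening of Protocol section 6 makes it binding: "Subjects who meet all the inclusion criteria and none of the exclusion criteria will be included in this study".

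No other section gives a magnesium or calcium limit. The protocol and SAP synopses mention only haematological, renal and hepatic function.

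Protocol 7.1.5 explains why these two electrolytes matter. For magnesium: "Progressive decreases in serum magnesium levels occur frequently, which can lead to severe hypomagnesemia". For calcium: "Hypocalcemia can also occur; in particular the frequency of severe hypocalcaemia may be increased when used in combination with platinum-based chemotherapy". It also asks for monitoring: "Serum electrolyte level determinations should be performed prior to treatment and periodically during treatment with cetuximab".

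The SAP synopsis, under its statistical considerations, confines the efficacy analysis to patients who met every eligibility criterion and had documented wild-type RAS.

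**The concern.** ULN is the top of the normal range. Used as a minimum, it excludes everyone in the normal range below it and admits only patients at or above the upper limit on both tests. That is the reverse of what a magnesium and calcium criterion should do in a cetuximab trial, where the risk is depletion.

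Two things are at stake:

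- **Entry.** A site applying the line literally would turn away patients with normal electrolytes.
- **Analysis set.** Because the SAP synopsis ties the efficacy set to the entry criteria, anyone auditing eligibility against the printed line would class patients with normal values as violators. SAP Table 5 has a row for eligibility deviations, so the question would come up.

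**Working it through.** The documents give no figure to reproduce. The check compares passages and then counts what each reading of the rule would admit.

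**Step 1. How the protocol uses limits elsewhere.**

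- In 6.1, the limits for neutrophils, platelets, haemoglobin and creatinine clearance are floors, and each prints a ≥ sign.
- Where another ULN limit prints a comparator, it is a ceiling: "Total bilirubin $< 1.5 \times \text{ULN" in 6.1 and, in the special-populations part of 7.1.5, "bilirubin \leq 1.5 times the upper limit of normal", with matching ceilings there for creatinine and transaminases.
- The magnesium and calcium line is the only one that combines ≥ with ULN.

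**Step 2. Which part of the line is wrong.** There are two candidates.

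- *The abbreviation is wrong (should be ≥ LLN).* This keeps the printed sign, matches the other floors in 6.1 and fits the low-value concern in 7.1.5. A translation slip is plausible, because Protocol Tables 4 and 7 leave the lower-limit abbreviation untranslated as LIN.
- *The sign is wrong (should be ≤ ULN).* This would match the other ULN ceilings but would admit patients with low values. It cannot be ruled out, because comparators are unreliable in this section. There are six multiplied ULN limits in 6.1: ASAT/ALAT at 2.5 and 5, bilirubin at 1.5, and alkaline phosphatase at 2.5, 5 and 10. Only bilirubin prints a comparator; compare "Alkaline phosphatase $2.5 \times \text{ULN".

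**Step 3. What each reading admits.** Class each electrolyte as L (below LLN), N (LLN to below ULN) or H (at or above ULN, with values exactly at ULN placed here). That gives 3 × 3 = 9 pairs, of which five contain a low value: LL, LN, LH, NL and HL.

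| Rule on both tests | Pairs admitted | Count | Normal/normal admitted? | Low-value pairs admitted |
|---|---|---|---|---|
| ≥ ULN (as printed) | HH | 1 of 9 | No | 0 of 5 |
| ≥ LLN | NN, NH, HN, HH | 4 of 9 | Yes | 0 of 5 |
| ≤ ULN | LL, LN, NL, NN | 4 of 9 | Yes | 3 of 5 |

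These are counts of combinations, not shares of patients. Only ≥ LLN both admits normal/normal and keeps out every low-value pair.

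**Step 4. Illustration in patients (assumed, not from the documents).** Suppose a proportion p of patients is at or above ULN on each test, with p between 1% and 10%.

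- If the two tests agree fully, the share passing the printed rule is p, or 1% to 10%. That means 1/p = 100 to 10 screened per eligible patient.
- If they are independent, the share is p², or 0.01% to 1%. That means 1/p² = 10,000 to 100 screened per eligible patient.

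The finding does not depend on this range. It shows only that the literal rule would be close to unworkable.

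**The case against.** The strongest objection is that this may not be an error in the plan at all. The text is a translation read by a program from PDF, and five of the six multiplied ULN limits in the same section print no comparator. If LLN became ULN in that process, the sponsor's document is correct. This cannot be excluded, and it is why checking the source comes first. It has not been shown either: a missing comparator is a different fault from a changed abbreviation, and here a complete limit with sign and reference is printed twice in one line.

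A second objection is that the rule was evidently not applied. The SAP reports 221 patients recruited and 181 in the efficacy analysis. Under the most favourable assumption above (p = 10%, full agreement), 181 eligible patients would need about 181 × 10 = 1,810 screened. It is reasonable to infer that sites did not use the printed limit, but the documents do not say which limit they did use. In addition, SAP 6.5.1.3 and 6.5.1.5 define the efficacy set by the absence of important deviations. The examples in 6.5.1.3 are RAS mutation, missing biomarker data and no cetuximab, with no laboratory limit. The effect on the analysis set is therefore conditional.

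Third, the SAP records the last patient as completing in June 2017, so a correction cannot change enrolment. The source-data-verification list in SAP Table 3 names LDH, creatinine, bilirubin and CEA for baseline biochemistry, not magnesium or calcium, so a later eligibility check would rest on values not named for verification. Both points stand. They limit what the correction can achieve but do not make the printed limit right.

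**Conclusion.** The concern holds. As written, 6.1 is a mandatory entry limit that rejects patients with normal magnesium or calcium below ULN, contradicts the safety reasoning in 7.1.5, and is corrected nowhere else. This much follows from the text alone.

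That the intended limit is ≥ LLN is an inference. It is well supported by the printed sign, the other floors in 6.1 and the hypomagnesaemia and hypocalcaemia warnings, but it is not stated. The cause (translation, typing or text extraction) is unknown.

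The size is minor. Protocol 8.1 schedules laboratory tests, including both electrolytes, within 7 days before treatment. Protocol 8.3 repeats them within 48 hours before each cycle, and 7.1.5 recommends replacement as needed. Alpha, power and sample size are unaffected. What remains is the accuracy of the record and a clear basis for judging this item when eligibility determines the efficacy set.

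**What to change.** 1. Check the magnesium and calcium limit in the source-language protocol.
2. If the slip is confirmed, correct the line in 6.1 so that both magnesium and calcium must be ≥ LLN. If the source shows a different limit, use that one.
3. Add one sentence to the SAP stating that this criterion is judged against the confirmed limit when the efficacy set and the eligibility deviations are determined, using the screening values scheduled in Protocol 8.1. Note that SAP Table 3 does not list these values for source verification.

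The cost is one document check, a one-line correction and one SAP sentence. No new data are needed and the sample size does not change.

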6.2 Exclusion criteria

PS $>$ 2 or elderly patients with frailty criteria, according to the investigator's criteria.

Previous surgery for metastases (liver, lung or other).

Patients who have received previous systemic treatment for metastatic colorectal carcinoma.

Pretreatment with anti-EGFr antibodies (eg, panitumumab) or treatment with small molecule EGFr tyrosine kinase inhibitors (eg, erlotinib) or EGFr signal transduction inhibitors. Subjects who discontinue their first dose of anti-EGFr therapy (panitumumab) due to an infusion reaction may participate in this clinical trial.

Metastases in the brain / central nervous system (exception: subjects who have been treated, have asymptomatic metastases in the central nervous system and have not received steroids for at least 30 days prior to study inclusion).

Previous malignant tumor within the last 5 years, except for a history of basal cell carcinoma of the skin or preinvasive cervical cancer.

Unresolved toxicities from prior systemic treatment that, in the opinion of the investigator, render the patient ineligible for inclusion.

Presence of peripheral neuropathy (grade $>$ 1 of version 3.0 of the common toxicity criteria (CCT)), and of serious wound or ulcer without healing or open bone fracture.

Hormone therapy, immunotherapy, or experimental or approved antibodies / proteins (eg, bevacizumab) \leq 30 days prior to enrollment.

Significant cardiovascular disease, including unstable angina or myocardial infarction within 12 months prior to the start of study treatment or a history of ventricular arrhythmia.

History of interstitial pneumonitis or pulmonary fibrosis or evidence of interstitial pneumonitis or pulmonary fibrosis on baseline chest CT scan.

Treatment for systemic infection within 14 days prior to the start of study treatment.

Acute or subacute bowel occlusion and / or active inflammatory bowel disease or other bowel disease causing chronic diarrhea (defined as > 4 loose stools per day).

History of Gilbert's syndrome or dihydropyrimidine deficiency.

History of any illness that may increase the risks associated with study participation or may interfere with the interpretation of the study results.

Known positive test for human immunodeficiency virus infection, hepatitis C virus with abnormal liver enzyme values, chronic active hepatitis B infection. Hepatitis C seropositive patients with normal liver enzyme values may be included.

Any concurrent illness that may increase the risk of toxicity.

The subject has a disorder of any kind that compromises their ability to provide written informed consent and / or comply with study procedures

Have received any investigating agent within 30 days prior to listing.

Pregnant or lactating woman, or planning to become pregnant within 6 months after the end of treatment.

Surgery (not including diagnostic biopsy or central venous catheter placement) and / or radiation therapy within 28 days prior to study enrollment.

Woman or man of childbearing potential who does not agree to take adequate contraceptive precautions, that is, to use 2 contraceptive methods together, at least 1 of them barrier (eg, contraceptive pills plus condom) or abstinence during over the course of the study and for 6 months after the last study drug administration for women and 1 month for men.

The subject is unwilling or unable to meet the requirements of the study.

Psychological, family, sociological or geographical conditions that potentially prevent compliance with the study protocol and the follow-up calendar. These conditions should be discussed with the patient before registering for the clinical trial.

6.3. Subject inclusions

Before the subjects can be included in the study, the sponsor needs to have a copy of the written approval of the protocol, the informed consent and the rest of the subject's information and / or inclusion material that may come from the Ethics Committee. Clinical Research Committee / Institutional Review Committee (CEIC / CRI) of the center and the AEMPS Approval.

Any subject who passes the selection period (defined as the moment the subject signs the informed consent) will be registered and will receive a unique identification number of the subject before any study procedure is performed. This number will be used to identify the subject throughout the clinical study and should be used in all study documentation related to that subject.

Study treatment should begin within 28 days of baseline CT.

6.4 Treatment assignment

The selection of treatment between FOLFOX-6 (m) + biweekly cetuximab or FOLFIRI (m) + biweekly cetuximab will be made by the Principal Investigator, according to the usual clinical practice of his center.

Single-arm, multicenter, prospective phase II clinical trial for biomarker validation in patients with advanced and / or metastatic colorectal cancer with non-mutated KRAS gene treated with chemotherapy plus biweekly cetuximab as first-line therapy

After confirmation of eligibility, the center's staff will fax an inclusion request form to the Sponsor (GEMCAD Technical Secretariat [REDACTED]) in which they must record the treatment chosen by the Principal Investigator for the patient.

The GEMCAD Technical Secretariat will return a communication to the center to confirm that a new patient has been registered in the study.

7. TREATMENT PROCEDURES

7.1. Dosage, Administration, and Biweekly Cetuximab Schedule

Cetuximab is commercially available. This drug will be formulated, packaged, labeled and stored according to the procedures indicated by the local manufacturer, the supplier and the center.

As it is a commercialized drug of habitual use in the study pathology, the supply will be carried out through the usual channels of the National Health System, with the prior favorable opinion of the CEIC and the approval of the Center's Directorate.

Cetuximab (Erbitux) should be administered under the supervision of a physician experienced in the use of antineoplastic pharmaceuticals. Close monitoring is required during the infusion and for at least 1 hour after the end of the infusion. Availability of resuscitation equipment must be ensured.

7.1.1. Dosage

Before the first infusion, the patient should be administered an antihistamine and a corticosteroid.

This premedication is recommended for all subsequent infusions.

Cetuximab will be administered every 2 weeks, the dose is 500 mg / m².

In reference to the dosage or modifications of the recommended dose of concomitantly used chemotherapeutic agents, consult the SmPC of these drugs. They should not be administered until one hour after the end of the cetuximab infusion.

Biweekly cetuximab treatment should be continued until underlying disease progresses.

Once a dose reduction has been made, a dose escalation will not be allowed in subsequent cycles.

In no case can the patient be kept in the study with Oxaliplatin or Irinotecan in monotherapy, or in combination with cetuximab without 5-FU.

7.1.2. Administration

Erbitux 5 mg / ml

Erbitux 5 mg / ml is administered intravenously via an infusion pump, gravity drip or syringe pump (for instructions for use and handling, see section 6.6 product data sheet).

The duration of the cetuximab infusion will be 120 minutes in the first cycle, 90 minutes in the second and 60 minutes from the third and later. The maximum infusion rate should not exceed 10 mg / min.

Prior to all cetuximab infusions, appropriate medication will be administered as a prophylaxis against the onset of acute hypersensitivity reaction. The patient should be given an antihistamine and a corticosteroid.

During the first infusion it is advisable for the doctor to be present or close to the treatment area. Patients will receive treatment in an area of the hospital where resuscitation equipment and other drugs are available for the treatment of acute hypersensitivity reactions, such as adrenaline or steroids. If an allergic reaction occurs to the infusion with cetuximab, the patient will be treated according to the best available medical practice. Patients will be asked to report delayed reactions to their physician immediately. Although it is not necessary to check vital signs, careful observation of the patient (up to one hour after the infusion) is required to monitor the possible appearance of AAs (specifically allergic reactions).

Erbitux can be given by gravity drip, infusion pump, or syringe pump. The infusion must be performed with a separate infusion line, which must be flushed with a sterile 0.9% (9 mg / ml) sodium chloride solution for injection at the end of the infusion.

Erbitux 5 mg / ml is supported

- with polyethylene (PE), ethyl vinyl acetate (EVA) or polyvinyl chloride (PVC) bags,
- with infusion sets made of polyethylene (PE), polyurethane (PUR), ethyl vinyl acetate (EVA), thermoplastic polyolefin (TP) or polyvinyl chloride (PVC),
- with polypropylene (PP) syringes for syringe pump.

Care should be taken to ensure aseptic conditions when preparing the infusion.

Erbitux 5 mg / ml should be prepared as follows:

- For administration with an infusion pump or gravity drip (diluted with sterile sodium chloride 9 mg / ml [0.9%] solution): Take one infusion bag of sodium chloride 9 mg / ml (0.9 %) sterile of the appropriate size. Calculate the required volume of Erbitux. Withdraw the appropriate volume of the sodium chloride solution from the infusion bag, using an appropriate sterile syringe with a suitable needle. Take an appropriate sterile syringe and attach a suitable needle. Withdraw the required volume of Erbitux from one vial. Transfer Erbitux to the prepared infusion bag. Repeat this procedure until the calculated volume is reached.

Connect the infusion line and prime with diluted Erbitux before starting the infusion. Use a gravity drip system or an infusion pump for administration. Set and control the speed as previously explained.

- For administration with an infusion pump or gravity drip (undiluted): Calculate the required volume of Erbitux. Take an appropriate sterile syringe (minimum 50 ml) and attach a suitable needle. Withdraw the required volume of Erbitux from one vial. Transfer Erbitux to an empty sterile

bag or container. Repeat this procedure until the calculated volume is reached. Connect the infusion line and prime with Erbitux before starting the infusion.

Set and control the speed as previously explained.

- For administration with a syringe pump: Calculate the required volume of Erbitux. Take an appropriate sterile syringe and attach a suitable needle. Withdraw the required volume of Erbitux from one vial. Remove the needle and insert the syringe into the syringe pump.

Connect the infusion line to the syringe, set and control the infusion rate as previously explained, and start the infusion after priming the line with Erbitux or sterile sodium chloride 9 mg / ml (0.9%) solution. . If necessary, repeat this procedure until the calculated volume has been infused.

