7.1.11. Cetuximab dose modifications for infusion-related reactions

If an infusion-related reaction occurs, the investigator should institute therapeutic measures corresponding to the best available medical practice. Based on previous experience with infusion-related reactions

Re-administration of treatment after an infusion-related reaction

Once the infusion rate of cetuximab has been decreased due to the occurrence of an infusion-related reaction, this decrease will continue during subsequent infusions. If a subject develops a second infusion-related reaction at the slower infusion rate, cetuximab should be permanently discontinued. If at any time a patient experiences a Grade 3 or 4 infusion-related reaction, cetuximab will be withdrawn from treatment. If there is any doubt as to whether a subject's reaction is a grade 1-4 infusion-related reaction, the study coordinator and / or principal investigator should be contacted immediately to discuss and grade.

Proposal to synchronize cetuximab and chemotherapy in case of delays

| | Week 1 | Week 2 | Week 3 | Week 4 | Week 5 | Week 6 | Week 7 | Week 8 | Week 9 | Week 10 | Week 11 | Week 12 |
|--------------------------------|--|--------|--------|--------|--------|--------|---|--------|--------|---------|---------|---------|
| Cetuximab (mg/m ²) | 500 | -- | 500 | -- | 250 | 250 | 500 | -- | 500 | 250 | 500 | -- |
| Chemotherapy | dose | -- | dose | -- | dose | dose | dose | -- | dose | -- | dose | -- |
| | Toxicity requiring delay in chemotherapy | | | | | | Cutaneous toxicity requiring delay in cetuximab | | | | | |

Whenever chemotherapy is administered, cetuximab will be administered at a dose of 500 mg / m² unless dermal toxicity precludes administration.

Whenever chemotherapy must be delayed, cetuximab will be administered at a dose of 250 mg / m² in order to allow the administration of 500 mg / m² one week later, coinciding with the planned administration of chemotherapy.

Provided that cetuximab has been delayed due to skin toxicity, but chemotherapy is given as planned, resolution of skin toxicity will be verified one week later. If appropriate, cetuximab will be administered at a dose of 250 mg / m² to allow a return to synchronous administration at the time of the next chemotherapy administration. It is recommended to use these same principles in anticipated cases of dose reduction of cetuximab.

Cetuximab dose reduction in case of skin reactions:

Other reasons to discontinue cetuximab;

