7.3.3 Dose levels and dose modification guidelines for the FOLFIRI regimen (m)

The toxicity of FOLFIRI (m) in subjects should be closely monitored. The doses of 5-FU and irinotecan can be adjusted according to the individual tolerance of each subject. The leucovorin dose will remain fixed at 400 mg / m² of racemate (d, l-leucovorin) or 200 mg / m² of l-leucovorin. Tables 5, 6 and 7 show the recommended dose levels and the guidelines for dose modification, due to neurological and non-neurological toxicity, for both irinotecan and 5-FU.

Table 6 describes the recommended dose reductions for non-neurologic toxicity.

Table 6. FOLFIRI dose reductions (m): non-neurological toxicity

| | Initial dose | Dose - 1 | Dose - 2 |
|------------|-----------------------|-----------------------|-----------------------|
| Irinotecan | 180 mg/m ² | 145 mg/m ² | 116 mg/m ² |

Single-arm, multicenter, prospective phase II clinical trial for biomarker validation in patients with advanced and / or metastatic colorectal cancer with non-mutated KRAS gene treated with chemotherapy plus biweekly cetuximab as first-line therapy

| | | | |
|------------|-----------------------|-----------------------|-----------------------|
| 5-FU Bolus | 400 mg/m ² | 320 mg/m ² | 240 mg/m ² |
|------------|-----------------------|-----------------------|-----------------------|

| | | | |
|---------------|-------------------------|-------------------------|-------------------------|
| 5-FU infusion | 2.400 mg/m ² | 1.900 mg/m ² | 1.500 mg/m ² |
|---------------|-------------------------|-------------------------|-------------------------|

Table 7 below describes the recommended dose modifications at the start of each subsequent therapy cycle. All dose modifications must be based on the worst preceding toxicity.

Single-arm, multicenter, prospective phase II clinical trial for biomarker validation in patients with advanced and / or metastatic colorectal cancer with non-mutated KRAS gene treated with chemotherapy plus biweekly cetuximab as first-line therapy

Table 7 FOLFIRI dose modifications (m)

Table 7 FOLFIRI dose modifications (m)

| Toxicidad | Nivel de dosis | En el momento del |
|---|--------------------------------------|--|
| Grado NCI* (valor) | para los ciclos posteriores | retratamiento |
| Toxicity | Dose level | In the moment of |
| Basado en la toxicidad del intervalo** | | |
| Absence of toxicity | Maintain the dose level | Maintain the dose level |
| Neutropenia (ANC) | | |

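### Two dosing instructions contradict themselves: at 500 mg/m² the 60-minute cetuximab infusion meets the 10 mg/min cap only up to 1.2 m², and FOLFIRI Table 7 names oxaliplatin where irinotecan belongs

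*Protocol*

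**What the plan says.** **Cetuximab infusion.** Protocol section 7.1.1 fixes the dose: "Cetuximab will be administered every 2 weeks, the dose is 500 mg / m²". Section 7.1.2 gives infusion times of 120 minutes for the first cycle and 90 for the second, and continues "60 minutes from the third and later. The maximum infusion rate should not exceed 10 mg / min". The preparation steps in the same section add only "Set and control the speed as previously explained". Lower doses arise in two places. Section 7.1.5, on repeated severe skin reactions, says "Treatment can be resumed at a lower dose (400 mg / m^2 after the second time" and allows 300 mg/m² after the third. Section 7.1.11 uses 250 mg/m² to bring delayed cetuximab and chemotherapy back into step. The SAP synopsis (test product row) reports the 120, 90 and 60 minute times in the past tense and does not mention the cap.

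**FOLFIRI dose reductions.** Section 7.3.3 says its tables guide modification "due to neurological and non-neurological toxicity, for both irinotecan and 5-FU". The table titled "Table 6. FOLFIRI dose reductions (m): non-neurological toxicity" lists irinotecan at 180, 145 and 116 mg/m², with two rows for 5-FU and none for oxaliplatin. Table 7, headed as the FOLFIRI modifications, links toxicity grade to action. Wherever it orders a reduction, the drugs named are 5-FU and OXAL. Its footnote 1, on mucositis, refers to oxaliplatin. Section 7.1.1 also sends sites to the product labels: "In reference to the dosage or modifications of the recommended dose of concomitantly used chemotherapeutic agents, consult the SmPC of these drugs".

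**The concern.** In section 7.1.2 a site is given a fixed time and a maximum rate. For a full-dose adult of ordinary size, the listed 60 minutes breaks the maximum. The step that should settle how fast to run the pump points back to the same two sentences. This is routine dosing from cycle 3 until progression.

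In FOLFIRI, Table 7 is the only table that ties a toxicity grade to a reduction. Read literally, it never lowers irinotecan after grade 3 or 4 neutropenia, thrombocytopenia or diarrhoea, or after febrile neutropenia.

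Both texts bear on patient safety. Protocol section 4.6.2 makes the safety profile of cetuximab 500 mg/m² every 2 weeks a secondary objective, and the SAP plans toxicity tables for treatment-related and cetuximab-related events. A reader of those tables would want to know how fast cetuximab was infused and whether irinotecan was reduced when it should have been. The documents do not settle either point.

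**Working it through.** **Part 1: time against cap**

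Inputs: dose 500 mg/m² (7.1.1); reduced doses 400 and 300 mg/m² (7.1.5) and 250 mg/m² (7.1.11); times 120, 90 and 60 minutes and cap 10 mg/min (7.1.2). The documents give no BSA distribution, so 1.6, 1.8 and 2.0 m² are assumptions. The protocol states no resulting rate or BSA limit that could be reproduced.

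Formulas:
- Rate (mg/min) = dose × BSA / minutes
- Largest BSA within the cap = 10 × minutes / dose
- Shortest time within the cap = dose × BSA / 10

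Largest BSA (m²) at which the listed time respects the cap:

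| Dose (mg/m²) | 60 min | 90 min | 120 min |
|---|---|---|---|
| 500 | 1.2 | 1.8 | 2.4 |
| 400 | 1.5 | 2.25 | 3.0 |
| 300 | 2.0 | 3.0 | 4.0 |
| 250 | 2.4 | 3.6 | 4.8 |

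Rates and times at the assumed BSA values:

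| Quantity | 1.6 m² | 1.8 m² | 2.0 m² |
|---|---|---|---|
| Rate, 500 mg/m² in 60 min (mg/min) | 13.3 | 15.0 | 16.7 |
| Excess over the cap | 33% | 50% | 67% |
| Rate, 500 mg/m² in 90 min (mg/min) | 8.9 | 10.0 | 11.1 |
| Rate, 400 mg/m² in 60 min (mg/min) | 10.7 | 12.0 | 13.3 |
| Shortest time, 500 mg/m² (min) | 80 | 90 | 100 |
| Shortest time, 400 mg/m² (min) | 64 | 72 | 80 |

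Over a wider assumed range the full-dose 60-minute rate runs from 500 × 1.4 / 60 = 11.7 to 500 × 2.2 / 60 = 18.3 mg/min, so every value exceeds the cap.

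If the cap is the mistake, it would need to be 500 × 2.0 / 60 = 16.7 mg/min for 60 minutes to hold up to 2.0 m². To match the 2.4 m² limit of the first cycle it would need to be 500 × 2.4 / 60 = 20 mg/min.

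**Part 2: FOLFIRI Table 7 against its own section**

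- Reduction cells in Table 7: neutropenia 2 (grades 3 and 4) + thrombocytopenia 2 + febrile neutropenia 1 + diarrhoea 2 = 7. All 7 name OXAL and none names irinotecan.
- Section 7.3.3 text and Table 6: 5-FU and irinotecan, no oxaliplatin.
- FOLFIRI composition (sections 3.3 and 7.3.2): irinotecan, leucovorin, 5-FU.
- FOLFOX Table 4 (section 7.2.3): the same seven cells and the same footnote 1, word for word. This fits a copy from that table.

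Worst case, a site that never lowers irinotecan because Table 7 does not say to: 180 / 145 = 1.241, so the patient receives 24% more than level -1.

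**The case against.** The strongest reply is that neither slip would mislead a competent site.

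*The cap.* It is a maximum placed directly after the times, and an upper safety limit is naturally read as overriding a nominal duration. That reading is safe and available, but no sentence states it, and the times are written as what will be done.

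*Table 7.* It gives no mg/m² values, so a site must open Table 6 even to reduce 5-FU, and Table 6 begins with irinotecan. A drug that is absent from the regimen cannot be reduced, so the slip is visible. This makes a full irinotecan dose after grade 3 or 4 toxicity unlikely, and the label referral in section 7.1.1 lowers the chance further. The 24% is therefore a worst case only. But Table 6 holds dose levels without toxicity triggers, so Table 7 remains the operative text and is wrong as written. A translation artefact in the public English text cannot be excluded: Table 7 has mixed Spanish and English headers.

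*The stopping rule.* Section 7.1.11 says "If a subject develops a second infusion-related reaction at the slower infusion rate, cetuximab should be permanently discontinued". Infusion rate enters that rule, but the rule works the same way whichever starting rate was used, so the link to the cap is thin. The point does not depend on it.

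*Lower doses.* At 300 and 250 mg/m², 60 minutes stays within the cap at all three BSA values in the rate table (1.6 to 2.0 m²). The conflict belongs to 500 and 400 mg/m².

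*Timing.* The SAP title page gives completion on 20 June 2017, so rewording protects no enrolled patient. What remains is an accurate record for the report and for anyone who reuses the regimen.

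**Conclusion.** Both contradictions stand. The BSA limits of 1.2 m² (60 minutes) and 1.8 m² (90 minutes) at full dose follow exactly from the protocol's own figures. Only the size of the excess rests on the assumed BSA values. The documents do not show whether the time or the cap is the mistake, nor what rate patients received. The Table 7 error is complete within the table: seven of seven reduction cells, plus the footnote.

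No harm to any patient is shown. Sample size, power and the primary biomarker and PFS analysis are unaffected. These are nonetheless wrong rules in operative dosing text that bears on safety, and they should be corrected.

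**What to change.** 1. **Section 7.1.2.** State that the 10 mg/min cap governs and that the listed times are minimums. The infusion then lasts at least dose × BSA / 10 minutes: 50 × BSA at 500 mg/m² and 40 × BSA at 400 mg/m². The same rule covers every lower dose. If the clinical leads conclude that the cap is the mistake, they should correct the cap instead.
2. **FOLFIRI Table 7.** Replace OXAL with irinotecan in the seven cells, and oxaliplatin with irinotecan in footnote 1, using the Table 6 levels. Check the Spanish site version first. If it is right, only the English text needs correcting.
3. **Study report.** Leave the SAP's past-tense infusion times as they are. Note both inconsistencies in the report. Where records allow, say which infusion rule was followed and whether irinotecan was reduced after grade 3 or 4 events. If infusion times were not recorded, say so.
4. **Clerical.** Section 3.3 gives the cetuximab solution as 2 mg/ml; section 7.1.2 and the SAP synopsis give 5 mg/ml. Correct section 3.3.

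The cost is wording in two protocol places, one clerical correction and a short note in the report. What the note can say depends on the records. Protocol section 12.1 names the amount used as a recorded item but not infusion duration. SAP Table 3 says dose modifications were source-checked only once all the listed variables had been reviewed for every patient at the site.
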